4.1.3. Study Day

The *study day* describes the relative day of an observation starting with the reference date designated as Study day 1. In this study, the Visit 2 (Baseline) date is the reference date. Thus, the study day will be calculated as:

- For days prior to the Visit 2 (Baseline) date, Study Day = Date – Visit 2 (Baseline) Date
- For days on/after the Visit 2 (Baseline) date, Study Day = Date – Visit 2 (Baseline) Date + 1

4.1.4. Out-of-Window Measurements, Analysis Visit, and Analysis Window

Analysis visit is a timing variable to be used for analyses involving visits. For each analysis visit, an *analysis window* is set up to determine the analysis visit to which a measurement should be mapped ([Table 3](#)).

The analysis visit of a measurement will be determined based on the study day of the measurement and specified analysis windows and is not necessarily the same as the study visit at which the measurement was collected. For example, an out-of-window measurement collected at the Week 2 study visit will be mapped to the Week 6 analysis visit, if the study day of the measurement falls into the analysis window of Week 6.

Table 3: Analysis Visit and Analysis Window

| Analysis Visit (Target Assessment Date) | Protocol Visit Window | Analysis Window |
|---|-----------------------|-----------------|
| Baseline (Day 1) | [1, 1] | - 1] |
| Week 2 (Day 15) | [13, 17] | [2, 28] |
| Week 6 (Day 43) | [40, 46] | [29, 57] |

In case that there are two or more visits that fall into the same analysis window, then the visit closest to the target assessment day will be selected for that visit window. In the case that two visits are equidistant to the target assessment day, i.e., one is before and one is after the target assessment day, the later one will be selected for that visit.

For analyses of IOP involving post-baseline visits, if there are two or more visits that fall into the same analysis window of a post-baseline visit, then the visit in which IOP are measured at all the scheduled timepoints (8:00, 12:00, and 16:00) will be selected for that analysis visit first, before applying the above rule.

Furthermore, if applying this analysis window results in missing IOP data, then the nominal visit will be used.

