3.4. Visits and Assessments

There are 4 scheduled visits for each subject. Assessments at each visit and the time/visit window for each post-baseline assessment are specified in the Assessment Schedule ([Table 2](#)). For subjects whose study participation is terminated prior to Week 6 (Visit 4, Day 43 \pm 3), to the extent possible, all assessments scheduled for Visit 4 will be performed at the Early Termination (ET) visit.

Table 2: Assessment Schedule

| | Washout Period | | Double-Masked Treatment Period | | |
|---|------------------------|--|--|--------------------------------|---|
| | Visit 1 (Screening) | Washout Period (up to 4 weeks) Optional Visit 1 ^k | Visit 2 Eligibility/ Baseline (Day 1) | Visit 3 Week 2 (Day 15±2) | Visit 4 Week 6 (Day 43±3) Exit or Early Termination ^l |
| Informed Consent(s) including the consent for pharmacogenomics/ genomics laboratory research study ^a | X | | | | |
| Inclusion/Exclusion Criteria | X | | X | | |
| Demographics and Medical History | X | | | | |
| Concomitant Medications / Therapies | X | X | X | X | X |
| Dosing Compliance | | | | X | X |
| Adverse Events | | X | X | X | X |
| Pregnancy Test ^b | X | | X | | X |
| Refraction ^c | X | | | | |
| BCVA ^c | X | X | X (prior to 8:00 IOP meas.) | X (prior to 8:00 IOP meas.) | X (prior to 8:00 IOP meas.) |
| Biomicroscopy ^d | X | X | X (prior to 8:00 IOP meas.) | X (prior to 8:00 IOP meas.) | X (prior to 8:00 IOP meas.) |
| IOP ^e | X (any time) | X (any time) | 08:00 12:00 16:00 | 08:00 12:00 16:00 | 08:00 12:00 16:00 |
| Pachymetry ^f | X | | | | |
| Instill study eye drop after 08:00 IOP measurement | | | | X (after to 8:00 IOP meas.) | X (after to 8:00 IOP meas.) |
| Gonioscopy ^g | X | | | | |
| Visual Field ^h | X | | | | |
| Ophthalmoscopy ⁱ | X (pupil dilation) | | X (after 16:00 IOP meas.) | | X (after 16:00 IOP meas., pupil dilation) |
| Blood Sampling for Pharmacogenomics/genomics ^j | | | | X | |
| Dispense Study Medication | | | X | | |
| Collect Study Medication | | | | | X |

Table 2: Assessment Schedule (Continued)

| | Washout Period | | Double-Masked Treatment Period | | |
|---|------------------------|--|--|------------------------------|---|
| | Visit 1 (Screening) | Washout Period (up to 4 weeks) Optional Visit 1 ^k | Visit 2 Eligibility/ Baseline (Day 1) | Visit 3 Week 2 (Day 15±2) | Visit 4 Week 6 (Day 43±3) Exit or Early Termination ^l |

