6.2. Handling of Missing Data

6.2.1. Efficacy Measure

For subjects with the use of any non-study IOP lowering therapy to lower IOP, unless otherwise specified, the IOP data collected after the non-study IOP lowering therapy will be censored (treated as missing) in efficacy analyses.

For each IOP endpoint, no imputation is needed for the analysis on observed cases using the mixed-effects model for repeated measures (MMRM).

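### The nominal-visit fallback in SAP 4.1.4 has no day limit and no Early Termination exclusion, so a reading from Days 2-28 can enter the primary MMRM as observed Week 6 data

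*SAP*

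**What the plan says.** SAP 4.1.4 makes the analysis visit depend on study day, so that it "is not necessarily the same as the study visit at which the measurement was collected". Table 3 of that section gives Days 2-28 to Week 2 (target Day 15) and Days 29-57 to Week 6 (target Day 43). Where several visits fall in one window, a visit with all three IOP timepoints is preferred, then the visit closest to target. As an illustration, the section says that "an out-of-window measurement collected at the Week 2 study visit will be mapped to the Week 6 analysis visit" if its study day falls there. The section closes with the fallback: "Furthermore, if applying this analysis window results in missing IOP data, then the nominal visit will be used".

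The assessment schedule in SAP 3.4 has no separate ET column; the heading is "Visit 4 Week 6 (Day 43±3) Exit or Early Termination". Protocol 8.1.5 combines Visit 4 and ET in the same way. The text of SAP 3.4 nevertheless speaks of ET as a visit: "all assessments scheduled for Visit 4 will be performed at the Early Termination (ET) visit".

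On missing data, SAP 6.2.1 says that for each IOP endpoint "no imputation is needed for the analysis on observed cases using the mixed-effects model for repeated measures (MMRM"). The same section sets to missing any IOP taken after non-study IOP-lowering therapy.

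**The concern.** The fallback has a sensible use. A Week 2 visit attended on Day 30, followed by Visit 4 on Day 43, would otherwise leave Week 2 empty. As written, though, it is not confined to that case. A subject who terminates before Day 29 has nothing in the Week 6 window. If that empty cell counts as missing IOP data and the ET visit is recorded as Visit 4, the rule fills Week 6 with a reading that the windows place in Week 2.

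Three things are at stake.

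- **Timing.** Protocol 4.2 justifies the treatment duration partly by an effect that stabilises within 4 weeks. The Week 6 window opens on Day 29, which is 29 - 1 = 28 days after Day 1. The fallback can admit earlier readings.
- **Selection.** Early leavers are not a random sample. Protocol 7.2.1 gives IOP above 34 mmHg as an example of lack of efficacy. SAP 6.2.1 removes readings taken after non-study therapy, but not an ET reading taken before it.
- **Transparency.** For the primary endpoint, Protocol 9.3.5 and 9.3.6.1 confine LOCF to sensitivity analyses. Here an early value would enter the primary model as an observed one. The code in SAP 12.1 selects on analysis visit and has no ET or study-day filter. The only sensitivity analysis of the primary endpoint (SAP 8.1.2) repeats the same model on the per-protocol set.

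**Working it through.** **The plan's own figure.** SAP 3.3 gives 50 per arm, SD 3.5 mmHg, a difference of 2.0 mmHg, two-sided alpha 0.05 and about 80% power. The standard error is 3.5 × √(2/50) = 0.70, and 2.0/0.70 = 2.857. Power is Φ(2.857 - 1.960) = 0.815 (0.808 with the noncentral t). The figure is reproduced, and 2.0 mmHg is used below as the yardstick.

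**What the rule does.** The windows and fallback were applied to ET visits on each day up to Day 70, without a Week 2 visit (from Day 2) and with one on Day 15 (from Day 16). Week 6 is otherwise empty and the ET IOP is usable.

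| Meaning of missing | Nominal label of ET | ET days used as Week 6, no Week 2 visit | ET days used as Week 6, Week 2 visit on Day 15 |
|---|---|---|---|
| Analysis visit is empty | Visit 4/Week 6 | 2-70 | 16-70 |
| Measurement lies in no window | Visit 4/Week 6 | 29-70 | 29-70 |
| Either | Its own label | 29-57 | 29-57 |
| No fallback at all | - | 29-57 | 29-57 |

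Only the first row is a problem for early readings. With visits on Day 15 and Day 20, both complete, Day 15 is chosen for Week 2 and the fallback makes Day 20 the Week 6 value. Even Day 16 would qualify. With no Week 2 visit, an ET reading on Days 2-28 fills Week 2 by window and Week 6 by fallback, and the SAP does not say whether it is moved or used twice.

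**Which meaning is more natural.** The post-baseline windows run without a gap from Day 2 to Day 57. If missing meant only a measurement outside every window, the sentence would act only after Day 57. An empty analysis visit gives it more to do. That reading, however, conflicts with the section's example: moving a late Week 2 reading to Week 6 empties Week 2 unless another reading fills it, and the fallback then sends the reading back.

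**Size, with assumed inputs.** Let k be the net excess of early terminators in one arm of n = 50, and gap their IOP excess over the arm mean, taken as equal at Week 2 and ET and after baseline adjustment. Let ρ be the Week 2 to Week 6 correlation, with equal variances at the two visits. The documents give none of k, gap or ρ.

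- Fallback value compared with a simple mean that omits these subjects: k × gap/n = 3 × 5/50 = 0.30 mmHg, which is 0.30/2.0 = 15% of the target.
- With Week 6 left missing, the MMRM already carries about ρ × k × gap/n through the Week 2 values. The extra shift from the fallback is therefore (1 - ρ) × k × gap/n. For ρ = 0.5 this is 0.5 × 0.30 = 0.15; for ρ = 0.7 it is 0.3 × 0.30 = 0.09 mmHg.
- Low case (2 subjects, 3 mmHg): 2 × 3/50 = 0.12, reduced to 0.036-0.06. High case (5 subjects, 8 mmHg): 5 × 8/50 = 0.80, reduced to 0.24-0.40 mmHg.

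**Power, also assumed.** Suppose 10% of each arm terminate before Day 29. If half of the 2.0 mmHg difference is present at ET, the fallback gives a difference of 2.0 × (1 - 0.10 × 0.5) = 1.90 and power 0.775. If none is present, it gives 1.80 and 0.730. Leaving these subjects out (45 per arm) gives 0.774. Power alone therefore does not decide the matter; the meaning of the Week 6 value does.

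**The case against.** The best defence is that the fault needs two facts the SAP does not state. ET may have its own label: SAP 3.1 lists it beside the scheduled visits, SAP 3.4 names an ET visit, and SAP 4.1.2 distinguishes Visit 4 for completers from an Exit Visit for those who discontinue. Missing may also refer to a measurement in no window, which would keep the fallback consistent with the worked example. Either fact removes the problem for Days 2-28. This stands as a limit on the claim. It does not settle the matter, because a rule governing the primary endpoint should not depend on unstated definitions.

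The defence is also right on reach. Protocol 7.2 expects withdrawal to be uncommon. Protocol 7.1 encourages subjects who stop the drug to attend the remaining visits, which would fill Week 6. After a Day 15 visit, the only exposed days inside the windows are 16-28, when no IOP visit is scheduled. A simple-mean calculation also overstates the shift, because it ignores the Week 2 data the MMRM uses.

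A reader might infer that the fallback undoes the windows altogether, so that ET readings from any day become Week 6 whenever Week 6 is empty. The documents do not support that. ET on Days 29-57 is Week 6 by Table 3 itself. The fallback does nothing when both analysis visits are filled. It also needs an ET reading that exists and has not been set to missing under SAP 6.2.1.

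**Conclusion.** The point holds in conditional form. On the more natural reading of missing, and if ET is recorded under the shared Visit 4/Week 6 column, an ET IOP from Days 2-28 can override the windows and be analysed as observed Week 6 data. On that same reading, the fallback also contradicts the section's example when the late reading leaves Week 2 empty.

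The size is not determined by the documents. The central illustration is 0.09-0.15 mmHg relative to an MMRM with Week 6 missing, or 0.30 mmHg if no Week 2 information is used. All of these rest on assumed numbers of terminators, IOP gaps and correlations. The direction depends on which arm has the excess.

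A reader might go further and conclude that the Week 6 contrasts are biased. That is not shown. It would require early terminations that differ between arms in number or IOP level, and leaving those subjects missing rests on its own missing-at-random assumption. Nor do the Week 6 contrasts alone decide the trial: SAP 6.4 requires significance at all six timepoints, three of them at Week 2. What is established is that a stated primary-endpoint rule can yield a mislabelled value, which is worth correcting before unmasking.

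**What to change.** Amend SAP 4.1.4 before unmasking as follows.

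1. Define missing IOP data: say whether it means an empty analysis visit or a measurement in no window.
2. Limit the nominal-visit fallback to a scheduled Visit 3 or Visit 4 attended out of window.
3. Assign ET and unscheduled IOP by study day only. If no reading falls in Days 29-57 and the limited fallback does not apply, leave Week 6 missing for the MMRM.
4. State that a reading moved by the fallback is used once only.
5. Align the worked example with the revised rule.

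The cost is a few sentences and a few Week 6 values that become missing. The fallback's useful purpose, keeping a late Week 2 visit as Week 2 when Visit 4 was also attended, is preserved.

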4.1.5. Out-of-Time-Window Measurements, Analysis Timepoint and Analysis Timepoint Window

Analysis timepoint is a timing variable to be used for analyses involving timepoints. In general, the analysis timepoint is the scheduled timepoint per protocol. For this study, the pre-specified IOP measurements time window in the protocol is (8:00±60 mins, 12:00 ±60 mins, 16:00 ±60 mins).

For each analysis timepoint, an *analysis timepoint window* is set up to determine the allowable range ([Table 4](#)).

Table 4: Analysis Timepoint and Analysis Timepoint Window

| Analysis Timepoint | Timepoint Window | Analysis Timepoint Window |
|--------------------|------------------|---------------------------|
| 8:00 | [7:00, 9:00] | - 9:59] |
| 12:00 | [11:00, 13:00] | [10:00, 13:59] |
| 16:00 | [15:00, 17:00] | [14:00 - |

If there are two or more measurements that fall into the same analysis timepoint window, the measurement closest to the target assessment time will be selected for that timepoint. In the case that two measurements are closest and equidistant to the target assessment time, i.e., one is before and one is after the target assessment time, the later one will be selected for that timepoint.

Furthermore, if applying this analysis timepoint window results in missing IOP data, then the nominal timepoint will be used for that visit.

4.2. Efficacy-Related Definitions

4.2.1. Study Eye and Fellow Eye

The study eye will be the eye that qualifies per eligibility criteria at Visit 2. If both eyes meet the eligibility criteria, the eye with the higher mean diurnal IOP at Visit 2 will be designated as the study eye. If both eyes meet the eligibility criteria and have the same mean diurnal IOP, the right eye will be designated as the study eye. The other eye will be the non-study eye, or fellow eye.

4.2.2. Efficacy Measure

IOP (measured in mmHg) is the efficacy measure for this study. For the IOP at each timepoint of measurement, a mean of two consecutive measurements using the Goldmann applanation tonometer will be used. If the two measurements differ by 2 mmHg or more, then a third measurement will be made, and the median of the three consecutive measurements will be used.

For the mean diurnal IOP, the mean of the three scheduled timepoints (8:00, 12:00, and 16:00) will be used.

4.2.3. Baseline Score

The *baseline score* is the observed measurement at Visit 2 (Baseline). If a baseline score is missing, the last observed measurement or derived score prior to the first dose of study medication will be used to impute the baseline score.

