 - If more than 10 letters in BCVA were lost compared to the screening visit, then refraction should be performed again.
 - Biomicroscopy (prior to the 08:00 IOP measurement)
- Perform IOP measurement at 08:00 (± 60 min).

- If subject meets the 08:00 IOP eligibility requirements, schedule additional IOP measurements at 12:00.
- Perform IOP measurement at 12:00 (± 60 min).
 - If subject meets the 08:00 and 12:00 IOP eligibility requirements, schedule additional IOP measurements at 16:00
- Perform IOP measurement at 16:00 (± 60 min).
- Perform ophthalmoscopy in both eyes after the 16:00 IOP measurement.
- Perform final review of eligibility criteria after the 16:00 IOP measurement and ophthalmoscopy. The subject will then be randomized, via Interactive Response Technology (Medidata Balance/RTSM).
- A subject who does not meet eligibility criteria or will not otherwise continue in the study is considered a screen failure.
- After the subject has been randomized to a treatment arm, and assigned a treatment kit by Balance/RTSM, a study staff member must:
 - Dispense the assigned kit to the subject which will contain the following;
 - Two (2) bottle of study drug labeled “morning”
 - Two (2) bottle of study drug labeled “evening”
 - Give the subject verbal and written instructions for proper instillation of the study medication, the dosing schedule and regimen, and study medication storage.
- Instruct the subject to instill the study medicine daily, starting from this evening (“evening” dose) (20:00).
- Schedule the subject to return on Day 15 ± 2 for Visit 3 (Week 2).
- Inform the subjects they will be reminded of the morning and evening instillation of the study medication by phone call a few days before Visit 3.
- Remind the subjects that the morning dose of Visit 3 will be done at the clinic.
- Remind the subject to bring all used and unused study medication at Visit 3.

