8.1.5. Visit 4 (Week 6, Day 43 ± 3) Study Exit/Early Termination

- Update concomitant medications and procedures/therapies.
- A study staff member should query the subject regarding dosing compliance.
 - If a subject deviates from the prescribed dosage regimen, the specific dates of the missed doses should be recorded.
- A study staff member **must** collect all used bottles of study medication.
- Query the subject regarding AEs.
- Obtain urine and perform urine pregnancy test, if the subject is a female of child-bearing potential.
- As per the SoA ([Table 3](#)) and Procedures of Assessments ([Section 8.2](#)), perform the following procedures or assessments immediately before the 08:00 IOP measurement (all ophthalmic procedures to be performed in both eyes):
 - BCVA (prior to the 08:00 IOP measurement)

- If more than 10 letters in BCVA were lost compared to the screening visit, then refraction should be performed again.
- Biomicroscopy (prior to the 08:00 IOP measurement)
- Perform IOP measurement at 08:00 (± 60 min).
- Instill study medication/eye drop after the 08:00 IOP measurement in both eyes. A study staff should make sure the instillation is performed.
- Perform IOP measurement at 12:00, and 16:00 (± 60 min).
- Perform pupil dilation in both eyes after the 16:00 IOP measurement.
- Perform ophthalmoscopy with pupil dilation in both eyes after the 16:00 IOP measurement.
- If the subject provided written consent to provide a blood sample for a future pharmacogenomics/genomics laboratory research study, the sample must be collected at this visit, if not collected at the previous visits.
- Exit the subject from the study.

Note: If a subject's study participation is terminated prior to Visit 4, then, to the extent possible, all scheduled Visit 4 procedures will be performed at the earliest visit or on the day of early termination.

Note: If subject requires an unscheduled visit, procedures and assessments will be performed as needed.

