8.2.2.9. Ophthalmoscopy (Fundus) Examination

The ophthalmoscopy (fundus) examination will be performed for each eye at Visit 1 (Screening), Visit 2 (Baseline, Day 1), and Visit 4 Study Exit/Early Termination, and graded as described

below. Ophthalmoscopy will be performed under dilation at Visit 1 (Screening) and Visit 4 Study Exit/Early Termination. Pupil dilation must be performed after all other ocular procedures have been completed. Cup to disc ratio and abnormality in retina, macula, choroid, and vitreous will also be evaluated.

Glaucomatous Optic Nerve Findings

The optic nerve will be evaluated using a 4-point scale (0-3 scale).

- None (0) = No damage
- Mild (1) = Optic nerve damage, secondary to glaucoma including any rim loss (sloping or thinning)
- Moderate (2) = Optic nerve damage, including cupping to disc margin at one or more points
- Severe (3) = Optic nerve damage, nearly total cupping, only nasal rim or less present

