| Phone call to remind subjects to take morning and evening dose on the day before each visit | | | | X | X |

^a Informed Consent(s) including the consent for pharmacogenomics/ genomics laboratory research study

Informed consent form (ICF) must be signed and dated before study procedures are performed. Informed consent for the optional pharmacogenomics/genomics laboratory research study may be obtained at any visit prior to study exit.

^b Pregnancy Test

A urine pregnancy test will be conducted for all female subjects of childbearing potential.

^c Refraction and BCVA

Refraction will be performed at the screening visit. If more than 10 letters in BCVA were lost compared to the screening visit, then refraction should be performed again. BCVA examination will be completed before IOP is measured at 08:00 (±60 min).

^d Biomicroscopy

Biomicroscopy examination must be completed before IOP is measured at 08:00. Aqueous flare and cell evaluation will be performed before fluorescein instillation.

^e IOP

IOP measurements will be performed at 08:00, 12:00 and 16:00 (±60 min) at all visits except for Visit 1 and optional Visit 1a (screening and mid-washout).

^f Pachymetry

Pachymetry will be performed after IOP measurement at Visit 1 (Screening).

^g Gonioscopy

If gonioscopy was performed within 3 months (90 days) prior to screening and was documented in the subject's records, no additional screening gonioscopy examination is necessary.

^h Visual Field

If visual field test was performed within 3 months (90 days) prior to screening and was documented in the subject's records, no additional screening visual field test is necessary.

ⁱ Ophthalmoscopy

Ophthalmoscopy will be performed at Visits 1, 2 and 4 (i.e. Screening, Baseline and Week 6) after the very last IOP measurement. Ophthalmoscopy will be performed with pupil dilation at Visit 1 and Visit 4/ Study Exit or Early Termination. Dilation of the pupil will be performed after the very last IOP measurement at Visit 1 and Visit 4/Study Exit or Early Termination.

^j Blood Sampling for Pharmacogenomics/genomics

Blood sampling for the pharmacogenomics/genomics laboratory research study may be performed at any visit after pharmacogenomics/genomics informed consent is obtained, subject is randomized and study drug, DE-117 ophthalmic solution 0.002%, dosing has begun.

^k Optional Visit 1a

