4. DEFINITIONS

4.1. Time-Related Terms

4.1.1. Baseline Visit

The *Baseline visit* is Visit 2 (Day 1) when the subject is randomized.

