9. SAFETY ANALYSES

Safety of DE-117 will be primarily assessed by AEs, BCVA and evaluation with slit-lamp biomicroscopy and ophthalmoscopy. The Safety population will be used for all safety summaries, where subjects will be classified by actual treatment received.

All the safety-related measures will be summarized descriptively by actual treatment received. Except AEs, the descriptive summary of each safety-related measure and the change from baseline in that measure will be performed if applicable.

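### Fundus change is measured from a Visit 2 examination done without dilation to a dilated Week 6 examination; a dilated Visit 1 to Visit 4/ET comparison should be added

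*SAP*

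**What the plan says.** **Examination schedule.** Ophthalmoscopy takes place at Visits 1, 2 and 4. Protocol 8.2.2.9 states: "Ophthalmoscopy will be performed under dilation at Visit 1 (Screening) and Visit 4 Study Exit/Early Termination". Footnote i to SAP Table 2 agrees: "Ophthalmoscopy will be performed with pupil dilation at Visit 1 and Visit 4/ Study Exit or Early Termination". The visit-by-visit instructions show the same contrast. For Visit 2 (Protocol 8.1.3) the step is "Perform ophthalmoscopy in both eyes after the 16:00 IOP measurement"; for Visit 4 (Protocol 8.1.5) it is "Perform ophthalmoscopy with pupil dilation in both eyes after the 16:00 IOP measurement", preceded by a separate dilation step.

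**Baseline.** Under SAP 4.1.1 the Baseline visit "is Visit 2 (Day 1) when the subject is randomized". Under SAP 4.2.3 the baseline score "is the observed measurement at Visit 2 (Baseline", and only when that value is missing is there a fallback: "the last observed measurement or derived score prior to the first dose of study medication will be used to impute the baseline score".

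**Analysis.** SAP 9 says that, for safety measures other than adverse events, "the descriptive summary of each safety-related measure and the change from baseline in that measure will be performed if applicable". SAP 9.3 tabulates ophthalmoscopy ratings by treatment and analysis visit, and summarises and lists any worsening of 2 units or more from baseline. SAP Table 5 gives the scales: optic nerve damage 0-3; cup/disc ratio to two decimals; retina, macula, choroid and vitreous 0 (normal) or 1 (abnormal).

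**The concern.** A change score should reflect change in the eye, not in the method of looking at it. Here the reference is the one scheduled fundus examination for which no dilation is specified, and the follow-up is dilated. An abnormality that was present all along, but not seen at Visit 2, can be rated normal at Baseline and abnormal at Week 6. Cup/disc ratio and optic nerve grade are exposed to the same change of method in every subject, not only in those with a lesion; the documents do not say in which direction it would move them.

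Ophthalmoscopy is a named safety endpoint, and Protocol 2.2 gives the purpose of the study as finding out whether BID dosing improves efficacy without compromising safety. With about 50 subjects per arm, a few artefactual findings would be visible in the fundus tables. A matching dilated pre-treatment examination is already collected, but the planned summaries leave it out.

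**Working it through.** **Step 1. Which examinations are compared?**

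| Examination | Dilation specified? | Role in the SAP |
|---|---|---|
| Visit 1 (Screening) | Yes | Fallback only, if Visit 2 is missing |
| Visit 2 (Day 1) | No | Baseline |
| Visit 4/ET | Yes | Post-baseline value |

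Neither document calls the Visit 2 examination undilated in so many words. This follows from dilation being listed for Visits 1 and 4 only, consistently across both schedules, the footnotes, the procedure section and the visit instructions.

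**Step 2. Do the by-visit tables avoid the problem?** No. SAP Table 3 has three analysis visits: Baseline, Week 2 and Week 6. There is no Screening visit. The lower limit of the Baseline window is not legible in the text reviewed. If it is open and Visit 1 falls inside it, the rule in SAP 4.1.4 selects the visit closest to target, which is Visit 2. Either way the tables place Visit 2 beside Week 6 and Visit 1 drops out.

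**Step 3. Which outputs can carry the artefact?**

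- Retina, macula, choroid, vitreous: largest possible increase is 1 - 0 = 1 unit, below the 2-unit threshold. They appear in the by-visit frequencies and any change summary, but cannot enter the worsening listing.
- Cup/disc ratio: recorded as a decimal (the SAP's example is 0.80), so a 2-unit rise is not realistic. It appears in any change-from-baseline summary.
- Optic nerve grade: largest possible increase is 3 - 0 = 3 units. It can enter the listing, but only with a jump of two grades.

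**Step 4. How large could it be?** The plan gives no fundus figure to reproduce. The only planning input used is the arm size of 50. It reproduces for IOP (difference 2.0 mmHg, SD 3.5 mmHg, two-sided 5%, 80% power): 2 x (1.960 + 0.842)^2 x 3.5^2 / 2.0^2 = 48.1, so 49 per arm, with power of about 0.81 at 50. The present point does not depend on it.

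For the fundus ratings let p be the proportion of study eyes with a pre-existing abnormality and m the proportion of those missed without dilation. **Both are assumptions; neither is in the documents.** Suppose nothing truly changes, the dilated examination sees every abnormality, and Visit 2 is graded without reference to Visit 1. Then

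expected apparent new findings per arm = 50 x p x m

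| p | m = 10% | m = 30% | m = 50% |
|---|---|---|---|
| 5% | 0.25 | 0.75 | 1.25 |
| 10% | 0.5 | 1.5 | 2.5 |
| 20% | 1.0 | 3.0 | 5.0 |

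The chance of at least one such finding in an arm, 1 - (1 - pm)^50, runs from 0.22 (pm = 0.005) to 0.995 (pm = 0.10). With the dilated Visit 1 examination as reference, the same model gives 0.

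**The case against.** **The baseline rule may not apply to safety data.** SAP 4.2.3 sits under the efficacy definitions. That is so, but the safety sections need a baseline, the SAP defines no other, and SAP 4.1.1 fixes Visit 2 separately. The inference is reasonable.

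**The worsening listing would not show it.** This stands for the four 0/1 items and, in practice, for cup/disc ratio (step 3). A reader might infer a run of false normal-to-abnormal macular or retinal entries in that listing; the 2-unit rule excludes it. SAP 9.3 names no shift table either, so the exposure is the by-visit frequencies and whatever change summaries are judged applicable.

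**Macular edema.** It is an event of special interest, so a reader might infer that those counts are distorted. The documents do not support this. Such events come from investigator reports, not from the baseline derivation. Presence, history or known risk factors of macular edema (exclusion 17) and potentially progressive retinal disease (exclusion 20) are screened at Visit 1, where the examination is dilated. The adverse event definition in Protocol Table 7 does admit conditions first detected after dosing that may have been there before, but an investigator holding the Visit 1 record can recognise an old lesion. The exclusions are not complete: stable retinal, choroidal and vitreous findings are not excluded as such.

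**Hiding or mimicking a drug effect.** A reader might infer a biased BID versus QD comparison. Both masked, randomised arms follow one schedule, and SAP 6 plans no statistical testing of safety measures. What remains is inflated counts in each arm and a noisier descriptive comparison.

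**The size is assumed.** This also stands. Nothing keeps the Visit 2 examiner from the Visit 1 record, which would lower the miss rate, and the lower end of the range is below one finding per arm.

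**Conclusion.** The mismatch is real and follows from the documents without any numerical assumption: the planned fundus comparison runs from an examination without specified dilation to a dilated one, although a matching pre-treatment examination exists. The consequence is limited to possible inflation of apparent on-treatment fundus change, in both arms alike, in descriptive tables. The range in step 4 is illustrative only, since the detection and prevalence rates behind it are assumed.

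It is also tempting to conclude that Visit 1 should replace Visit 2 as the fundus baseline. The documents do not support going that far. Visit 1 may be up to about 35 days before dosing and precedes washout of prior IOP-lowering medication. Using it alone would attribute any change over that interval to the treatment period and discard the last pre-dose examination. The sound form is an added comparison.

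**What to change.** In SAP 9.3:

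- Add Screening (Visit 1) as a displayed visit for all ophthalmoscopy parameters.
- Summarise change or shift from the dilated Visit 1 examination to the dilated Visit 4/ET examination, by treatment and eye, and label it as the like-for-like comparison.
- Keep the Visit 2 results alongside, with a note that no dilation was specified at that visit.
- State in SAP 4.2.3 or 9.3 which baseline each ophthalmoscopy summary uses, including the worsening listing.

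No procedure changes and no new data are needed; the cost is some table and derivation work before the SAP is finalised. The drawback is the age of the Visit 1 reference and its position before washout, which is why Visit 2 should stay in the display.
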